# **METHODOLOGY**

Please refer to instructions when completing this form. The application must be typed using a font no smaller than 11-point.

### 1. Describe the purpose of study, including research questions and/or hypotheses.

**Purpose**: The purpose of this pilot study is to examine the feasibility and efficacy of a noninvasive brain stimulation technique, repetitive transcranial magnetic stimulation (rTMS) in dual-task walking in individuals post-stroke. Our long-term objective is to use the technique as an adjunct rehabilitative tool to enhance gait recovery after stroke.

**Background**: Control of human movements requires sophisticated coordination between motor system and cognitive system. In able-bodied, the interaction between the two systems is often faultless and allows automatic execution of well-learned motor skills, such as walking. However, such coordinated interaction is often disrupted after brain insults (e.g. stroke). Numerous studies have shown that patients with stroke have difficulty in dual-task performance, for instance talking while walking. Therefore, dual-tasking has been deemed as an important outcome to determine the effectiveness of gait rehabilitation. To date, there is very limited research on how to enhance dual-task gait in stroke.

Non-invasive brain stimulation, such as rTMS, has been found to be an effective adjunct tool to traditional behavioral training to improve recovery of arm-hand function after stroke. rTMS can be used to up-regulate or down-regulate the excitability of the targeted neural network and subsequently affect the behaviors supported by that neural network. For example, in a previous research we applied 5Hz rTMS on the primary motor cortex (M1) in young healthy adults and found that it significantly increased M1 excitability. Similarly, we demonstrated that application of 1Hz rTMS on the dorsal premotor cortex (dPM) significantly decreased corticospinal excitability and interfered with participant's ability to learn the motor task under dual-task conditions. Although the efficacy of rTMS has been well-demonstrated in recovery of upper extremity motor function after stroke, its usefulness for gait recovery is understudied.

There have been attempts to use non-invasive brain stimulation to improve dual-task walking in humans, including neurological involved population. To date, there is no study that examines the efficacy of non-invasive brain stimulation in dual-task walking in individuals post-stroke. In addition, previous research has primarily focused on stimulating left dorsal lateral prefrontal cortex (DLPFC). Most studies found that up-regulating excitability of the left DLPFC improved dual-task cost but had little effect on gait performance. One possible explanation is that the DLPFC does not play an important role in governing gait performance during dual-tasking even though it has significant impact on task switching. Therefore, other neural networks, such as the supplementary motor area (SMA) that has been found to be associated with gait recovery may also play an important role in modulating dual-task gait. The purpose of this pilot project is to examine the efficacy of rTMS applied to different neural loci in improving dual-task gait in individuals post-stroke.

**Research question:** Would rTMS applied to different neural loci result in different dual-task gait performance in patients with stroke?

# 2. Participant Information:

a. Description of participants in study:

Ten men and women with a diagnosis of left hemisphere stroke and age >18 years will be recruited to participate in this pilot project.

- b. Approximate number of participants: 10
- c. Vulnerable populations as participants (check all that apply):

Prisoners[	
Pregnant women	
Fetuses / neonates	
Minors	

NOTE: Researchers must comply with the federal mandate to report child abuse. See instructions for details.

d. Age (or age range) of participants: > 18 years

Provide the rationale for inclusion/exclusion on the basis of age:

- 1. This study will not include individuals age below 18 years for a few reasons. Stroke is relatively uncommon in persons younger than 18 years. Further, rTMS safety data in children and adolescents are less well-established. We exclude individuals younger than 18 years for both scientific merit and safety concern.
- e. Sex of participants ...... Both

Provide the rationale for inclusion/exclusion on the basis of sex:

If yes, provide a description of the exclusion criteria and the rationale for using these criteria:

g. List and provide rationale for any other inclusion/exclusion criteria:

Inclusion criteria:

- Age above 18 years
  Stroke is very unlikely in individuals age below 18 years. Further, there are limited data to support the safety of rTMS in individuals younger than 18 years.
  - Diagnosis of Left hemispheric stroke at least 6 months ago
    Left dorsolateral prefrontal cortex has been shown to play an important role in human dual-task performance. We therefore specifically target those with left hemispheric lesion since they demonstrate greater deficits in dual-tasking. We exclude acute and subacute (< 6 months) stroke because spontaneous recovery is very likely to occur

during acute and subacute phases. This will lead to difficulty in result interpretation with the current single group design.

- First time stroke OR complete gait recovery from prior stroke
  Individuals with more than one stroke often have more than one lesion location or involve more than one hemisphere. This would potentially complicate the rTMS application. We therefore exclude those with multiple strokes such that our sample can be more homogenous.
- 4. Able to walk independently for at least 10 meters with or without walking aids 2.Participants are required to walk independently for the behavioral testing.
- 5. Have at least minimal movements (> 5 degree of motion) at the affected ankle 2.Stroke survivors with big lesions at the motor areas often have difficulty to actively control distal segments (hands or ankle) and show very little responses to TMS stimulation. In our past experience, we found that resting motor threshold cannot be reliably measured in those with very little active movements.
- Score > 26 on Mini Mental State Exam (MMSE)
  2.Participants are required to score > 26 to rule out any cognitive impairments that would interfere with their comprehension of instructions.
- 7. Ability to participate in the informed consent process

Exclusion criteria:

- Diagnosis of other neurological conditions, such as Parkinson Disease, Alzheimer, Spinal Cord Injury, Multiple Sclerosis
   2.This is to ensure that our sample is representative of stroke.
- Other comorbidities which could interfere with gait (i.e. amputation, severe osteoarthritis)
  2.This is to ensure that any potential gait deviations observed can only be attributed to stroke.
- Unstable clinical conditions
  This is to ensure safety during testing. Individuals with unstable clinical conditions, eg. uncontrolled hypertension, will not be included.
- Non-ambulatory prior to onset of stroke
  This is to ensure that any potential gait deviations observed can only be attributed to stroke.
- History of significant head trauma
  This is a contraindication of high frequency rTMS.
- Electrical, magnetic, or mechanical implantation: cardiac pacemakers or intracerebral vascular clip
   This is a contraindication of TMS.
- 7. Metal implantation in the oral cavity, head/neck area and lower extremity 2. This is a contraindication of TMS.

- Pregnancy
  2.This is a contraindication of TMS.
- 9. History of seizures or unexplained loss of consciousness 2. This is a contraindication of TMS.
- 10. Immediate family member with epilepsy 2.This is a contraindication of TMS.
- 11. Use of seizure threshold lowering medicine 2. This is a contraindication of TMS.
- 12. Current abuse of alcohol or drugs 2. This is a contraindication of TMS.
- 13. Anticipated inability to complete the study2. This is to ensure that participants can complete the study (all 3 visits).
- 14. History of psychiatric illness requiring medication control

2. This is a contraindication of TMS.

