# 3. Describe the participant recruitment process in detail. Make sure that you attach any recruitment materials or scripts in the attachment section.

Research participants will be recruited through local advertising and word-of-mouth by PI and research assistants (advertising flyer attached). The potential participants will contact the PI or research assistants via email, phone or face-to-face for a short meeting within which the research project will be explained by the PI or the research assistants using the Consent Form as a guide. This meeting will take approximately 10-15 minutes. It should be noted that if the participant indicates he/she does not wish to participate after the meeting, he/she would not be enrolled. The signed consent will be obtained upon the agreement to participate. The original consent will be kept in the research file, one copy will be placed with the PI and the participant will receive a copy.

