During each visit, they will receive 5Hz rTMS delivered to the target area (hot spot of the right tibialis anterior at the M1, left SMA, or left DLPFC). The 5Hz rTMS will be delivered in the form of 24 10-second trains with a 30second intertrain interval (a total of 1200 pulses) via a airfilled figure of 8 coil (Figure 2). The stimulation intensity will be set at 90% of individual RMT. We have previously shown that this protocol was effective to upregulate corticospinal excitability.

Figure 2. Air-filled coil for rTMS

After the rTMS protocol, corticospinal excitability will be reassessed using single pulse TMS again (procedure 2c). Participants will then perform the gait assessment (procedure 2a) and the counting task (procedure 2b).

Each participant will be tested for 3 visits (each visit will be 7±2days apart between two successive visits). Each visit will start with the assessment and be followed by a rTMS protocol. The target area for the rTMS protocols varies across visits (e.g. visit 1: Left SMA, visit 2: Left M1, and visit 3: Left DLPFC). The order will be pseudo-randomized and counterbalanced within each group.

4. Outcomes and data analysis: The primary outcome of this project is participant performance on the TUG test under single and dual-task conditions. The time taken to complete the TUG test under the two conditions will be used to derive dual-task cost (TUGdual – TUGsingle/TUGsingle). The dual-task cost will be compared across three rTMS protocols using repeated measure ANOVA. The secondary outcomes of the projects include gait parameters obtained from the

The secondary outcomes of the projects include gait parameters obtained from the GaitRite, MEPs measured under procedure 2c. These measures will be analyzed using repeated measure ANOVA as well.

b.	Is video recording a part of the s	tudy?	🛛 Yes 🗌 No	
	With sound $\square$	Without sound		
C.	Is audio recording a part of the s	tudv?		Yes 🗆 No

*If you answered "yes" to question #4b or 4c, describe the purpose of the recording and who will have access to these recordings.* 

The video recording will be used to quantify the number of corrected responses participants made on the counting task.

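### Does the stroke-history criterion contradict its own rationale badly enough to need a change to the plan?

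*Combined protocol and SAP*

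**What the plan says.** The combined protocol and SAP is an institutional review form. Section 2, item g asks the applicant to "List and provide rationale for any other inclusion/exclusion criteria", so each entry is a criterion followed by an explanation.

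The stroke-history entry, under the inclusion criteria, reads "First time stroke OR complete gait recovery from prior stroke". Its explanation has three steps:

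- a premise about lesions: "Individuals with more than one stroke often have more than one lesion location or involve more than one hemisphere";
- a consequence for the intervention: "This would potentially complicate the rTMS application";
- a conclusion: "We therefore exclude those with multiple strokes such that our sample can be more homogenous".

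A separate inclusion criterion requires a left-hemisphere stroke six months or more before entry. It does not limit the number of strokes. The planned size is given as "Approximate number of participants: 10".

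Section 4 has each participant attend three visits with a different stimulation target at each, for example "visit 1: Left SMA, visit 2: Left M1, and visit 3: Left DLPFC". Dual-task cost is compared across the three targets by repeated-measures ANOVA.

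**The concern.** The second branch of the criterion has work to do only for someone who had a stroke before the qualifying one. It therefore admits people with at least two strokes, and the sentence beneath says such people are kept out. The stated reason makes the clash sharper. It concerns how many lesions there are and which hemispheres they occupy, and regained gait changes neither. Even if the criterion governs, its explanation argues against part of it.

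At stake is a clear entry rule in a very small sample. If screeners followed different sentences, similar people could be treated differently. If extra lesions altered the response to one target more than to another, the within-person comparison would not remove that difference. The stated wish for a homogeneous sample would be weakened.

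**Working it through.** The plan gives no figure to reproduce on this point, so the check is one of logic.

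**Step 1. Apply each sentence to each stroke history.** Assume throughout that the person also has the required left-hemisphere stroke.

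| Stroke history | Criterion line | Closing sentence of the rationale |
|---|---|---|
| First stroke only | admits | admits |
| Earlier stroke, gait not fully regained | excludes | excludes |
| Earlier stroke, gait fully regained | admits | excludes |

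The sentences agree on two of the three histories and disagree on the third, which is the group the second branch was written for. The inconsistency is confirmed.

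**Step 2. Look for text that settles it.** The 14 exclusion items contain nothing on earlier or repeated stroke. The nearest, on other neurological conditions, lists different diseases. The screening step in Section 4 names a cognitive test, a TMS safety questionnaire and a 10-metre walk, and none is described as deciding stroke history. No other text says which sentence governs.

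**Step 3. Ask whether the rule can be applied.** The form separates criterion from explanation. The criterion line is the only listed rule on stroke history, and the table shows that it gives an answer in every row. A screener working from the list would reach a definite decision, and the explanation then omits the exception made just above it. That the criterion governs is an inference from the form's layout. The document does not say so.

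**Step 4. Ask whether applying the listed criterion harms the primary comparison.** Write the outcome of person i at target j as

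y_ij = a_i + t_j + g_ij + e_ij,

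where a_i is the person's stable level, t_j the target effect, g_ij any person-specific response to that target, and e_ij error. The difference between targets j and k within person i is

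y_ij − y_ik = (t_j − t_k) + (g_ij − g_ik) + (e_ij − e_ik).

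The level a_i cancels, so an earlier stroke that only raises or lowers a person's dual-task cost overall does no harm. A target-specific response g_ij does not cancel, and extra lesions could in principle act through it. The document gives no size for such a response and no expected number of people affected. Nor is this kind of variation confined to people with an earlier stroke. The criteria fix the hemisphere of the qualifying stroke but not the lesion site within it, so first-stroke participants may also differ in how their lesions lie relative to the three left-hemisphere targets.

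**Step 5. Note what limits the practical difficulty.** Everyone must walk independently and have some active movement at the affected ankle. Neuronavigation is specified for placing the TMS coil, and rTMS intensity is set from the individual's own motor threshold. These do not answer the lesion concern in full, but they bear on whether stimulation can be applied.

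**The case for a change.** The best argument for acting is that the text is wrong on its face and cheap to put right. One or two lines would do it, and the rule decides who enters a trial of about ten people. The lenient reading, that the closing sentence means only those outside the exception, does not fully repair the text because lesions and gait are different things. Section 3 also says "Research participants will be recruited through local advertising and word-of-mouth by PI and research assistants", so more than one person may meet the ambiguity.

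Part of this stands. The wording is inconsistent, and the rationale does not explain why regained gait is enough.

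The rest is weaker:

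- **Homogeneity.** The closing sentence also gives homogeneity as an aim. In a gait study, requiring full recovery from the earlier stroke plausibly serves that aim. Two of the listed exclusions rest on similar reasoning, that gait deviations should be attributable to stroke. The lesion argument is itself hedged. An incomplete justification is a lesser fault than an unusable rule.
- **Several screeners.** Section 3 concerns recruitment, explanation of the study and consent. Section 4 places screening after consent and does not say who does it. Inconsistent application is conjecture.
- **Small sample.** One participant is 1/10 = 10% of the sample, but that is true of any participant and says nothing about this group in particular.

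**Conclusion.** The inconsistency is genuine but clerical: an explanatory sentence is broader than the criterion it explains. It affects one of three stroke histories and an unstated number of people, possibly none. No bias in the comparison of targets is shown, and following the listed criterion is not shown to give a wrong or worse result in this within-person pilot.

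The two sentences should say the same thing, and which rule is meant is for the investigator to settle. Either way, rewording leaves the targets, visits, outcome and analysis as they are, so no change to the plan is called for.

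This rests on two assumptions. The first is that the listed criterion is treated as the operative rule, which the form's layout suggests but the document does not state. The second is that few participants, if any, fall in the disputed group, on which the document is silent. Evidence that such people were numerous and responded differently by target would reopen the question. The document contains none.

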# 3. Describe the participant recruitment process in detail. Make sure that you attach any recruitment materials or scripts in the attachment section.

Research participants will be recruited through local advertising and word-of-mouth by PI and research assistants (advertising flyer attached). The potential participants will contact the PI or research assistants via email, phone or face-to-face for a short meeting within which the research project will be explained by the PI or the research assistants using the Consent Form as a guide. This meeting will take approximately 10-15 minutes. It should be noted that if the participant indicates he/she does not wish to participate after the meeting, he/she would not be enrolled. The signed consent will be obtained upon the agreement to participate. The original consent will be kept in the research file, one copy will be placed with the PI and the participant will receive a copy.

# 4. Research Procedures:

- a. In the space below, describe in detail the research procedures (do not use an attachment):
  - Screening and Baseline assessment: Upon the consent, participants will be screened for their eligibility in addition to the criteria. We will use Mini Mental State Exam (MMSE; 3.Appendix 1) and TMS safety-screening questionnaire (3.Appendix 2) to ensure that participants do not have any cognitive impairments or contraindications for TMS. In addition, they will be asked to perform a 10 meter walk test to ensure they are able to walk 10m independently.

Once the eligibility is determined, each participant will be assessed with the Fugl-Meyer Motor Assessement (FMA; 3.Appendix 3) scale to quantify their motor impairment and a Trail-Making Test (TMT; 3.Appendix 4) to assess their executive function.

2. **Assessements**: Each participant will be tested with a gait assessment, followed by a counting task performance and a neurophysiological assessement.

2a. Gait Assessment: The gait assessment consists of walking at self-selected speed on the GaitRite carpet walkway. Gait performance (time taken, gait speed, stride cycle, step length) will be recorded by the GaitRite. The assessment will be repeated 3 times with about a 1 minute break between trials.

The walking test will then be repeated for another 3 trials under a dual-task condition in which the participants will perform the walking task in conjunction with a counting task. Before the 'Go' command, the tester will verbally provide a random number ranged from 30 to 100. They are then asked to perform the TUG test and count backward by 3 from the given number (e.g. 87, 84, 81, ...). During the dual-task TUG test, the participants will be asked to priortize the counting task.

In addition to the GaitRite measurement, the gait assessment will be videorecorded such that participants' performance on the counting task can be quantified offline (number of correct responses).

2b.Counting Task assessment: After the participants finish the gait assessment, the counting task will be repeated 3 times while they are seated.

2c. Corticospinal excitability assessment: After the counting task assessment, participants will go through a series of corticospinal excitability assessement using single pulse transcranial magnetic stimulation (TMS, MagstimR Company, UK) . Surface electromyography (EMG) electrodes will be placed on the right Tibilias Anterior muscle with the participants seated on a reclining chair and wearing a pair of earplugs. EMG data will be sampled at 2000Hz and band-pass-filtered at 15-500Hz (Mega 600, Mega Electronics Ltd, Finland). The EMG data will be recorded and stored using MegaWin software (Mega Electronics Ltd, Finland) and analyzed offline using Matlab program (The Mathowroks, Inc, Natick MA). A Magstim 200 stimulator (Magstim Company, UK) will be used to deliver the TMS pulse via a double cone coil (Figure 1).

Figure 1. Double cone coil.

Neuronavigation system Brainsight TM (Rogue Research, Canada) will be used to reliably place the TMS coil over the scalp to precisely target the selected area. Stimulation will begin at 40% of maximum stimulator output and will be systematically increased to yield a motor evoked potential (MEP) from the tibialis anterior. A 'hot spot'of the right tibialis anterior will first to be determined. Hot spot is defined as the site at which the largest MEP is obtained at the lowest TMS stimulation intensity. Once the hot spot is determined, the resting motor thershold (RMT) will be defined. Resting motor threshold is the stimulation intensity that yield a MEP peak-to-peak amplitude > 50  $\mu$ V in 5 out of 10 consecutive trials. Once RMT is decided, the stimulation intensity

will be set at 120% RMT and 10 stimulations will be delivered to the hot-spot such that suprathreshold MEP can be recorded. These MEPs measures will be stored and analyzed offline to quantify corticospinal excitability.

3. **rTMS protocols:** After the corticospinal excitability assessment, participants will receive a high frequency rTMS applied to different areas at different visits.

During each visit, they will receive 5Hz rTMS delivered to the target area (hot spot of the right tibialis anterior at the M1, left SMA, or left DLPFC). The 5Hz rTMS will be delivered in the form of 24 10-second trains with a 30second intertrain interval (a total of 1200 pulses) via a airfilled figure of 8 coil (Figure 2). The stimulation intensity will be set at 90% of individual RMT. We have previously shown that this protocol was effective to upregulate corticospinal excitability.

Figure 2. Air-filled coil for rTMS

After the rTMS protocol, corticospinal excitability will be reassessed using single pulse TMS again (procedure 2c). Participants will then perform the gait assessment (procedure 2a) and the counting task (procedure 2b).

Each participant will be tested for 3 visits (each visit will be 7±2days apart between two successive visits). Each visit will start with the assessment and be followed by a rTMS protocol. The target area for the rTMS protocols varies across visits (e.g. visit 1: Left SMA, visit 2: Left M1, and visit 3: Left DLPFC). The order will be pseudo-randomized and counterbalanced within each group.

4. Outcomes and data analysis: The primary outcome of this project is participant performance on the TUG test under single and dual-task conditions. The time taken to complete the TUG test under the two conditions will be used to derive dual-task cost (TUGdual – TUGsingle/TUGsingle). The dual-task cost will be compared across three rTMS protocols using repeated measure ANOVA. The secondary outcomes of the projects include gait parameters obtained from the

The secondary outcomes of the projects include gait parameters obtained from the GaitRite, MEPs measured under procedure 2c. These measures will be analyzed using repeated measure ANOVA as well.

b.	Is video recording a part of the s	tudy?	🛛 Yes 🗌 No	
	With sound $\square$	Without sound		
C.	Is audio recording a part of the s	tudv?		Yes 🗆 No

*If you answered "yes" to question #4b or 4c, describe the purpose of the recording and who will have access to these recordings.* 

The video recording will be used to quantify the number of corrected responses participants made on the counting task.

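### The primary endpoint is built on TUG time in both task conditions, but procedure 2a describes no single-task TUG trial and does not settle which motor test is timed

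*Combined protocol and SAP*

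**What the plan says.** Section 4, item 4 (Outcomes and data analysis) states: "The primary outcome of this project is participant performance on the TUG test under single and dual-task conditions". Completion times in the two conditions are turned into a dual-task cost, which is compared across the three rTMS target sites by repeated measures ANOVA. Gait parameters from the GaitRite are listed separately, as secondary outcomes.

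The measurements come from Section 4, procedure 2a (Gait Assessment). Its single-task part reads: "The gait assessment consists of walking at self-selected speed on the GaitRite carpet walkway". It adds: "Gait performance (time taken, gait speed, stride cycle, step length) will be recorded by the GaitRite". Three such trials are planned. For the dual-task part it says "The walking test will then be repeated for another 3 trials under a dual-task condition", and shortly afterwards, of the same trials, "They are then asked to perform the TUG test and count backward by 3 from the given number".

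Item 3 applies the same procedure after stimulation: "Participants will then perform the gait assessment (procedure 2a) and the counting task (procedure 2b". Whatever 2a leaves open before rTMS is therefore also open after it.

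**The concern.** A dual-task cost is a relative change, so it has meaning only if the numerator and the denominator come from the same motor task. Item 4 says that task is the TUG. Procedure 2a attaches the name TUG to the dual-task trials only and describes the single-task trials as walking on the GaitRite walkway. Taken together, the two places do not tell a tester which test to run without counting, or an analyst which recorded time belongs in the denominator. Because this is the primary endpoint, the gap affects the main comparison of the study.

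**Working it through.** The plan gives no TUG or walkway times, so there is no figure to reproduce. The check is a comparison of the text.

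**1. What each place supplies**

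| Quantity needed by item 4 | What procedure 2a provides |
|---|---|
| Single-task TUG time | Not described. The three single-task trials are self-selected-speed GaitRite walks with a recorded time. |
| Dual-task TUG time | Three trials, named once as a repeat of the walking test and once as the TUG. |
| What the TUG consists of | Not described: no course, start and stop rule, or timing method. |

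**2. Whether another section fills the gap**
- The 10-metre walk in the screening paragraph of Section 4 is an eligibility check.
- The Fugl-Meyer and Trail-Making Test are baseline measures and give no TUG time.
- The attachment list in Section 16 names no TUG instrument, and the form asks for procedures to be described in place, without an attachment.
- The loss-of-balance row of the risk table (Section 7) says the gait assessment includes turning as well as walking. That is compatible with a TUG but names none.

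**3. The possible readings**
- *One common test, loosely named.* Procedure 2a presents the dual-task trials as a repeat: "The walking test will then be repeated for another 3 trials under a dual-task condition". The sentence "In addition to the GaitRite measurement, the gait assessment will be videorecorded" suggests that the counting trials also take place on the walkway. The mention of turning fits this reading if the common test is a TUG.
- *Single-task TUG trials are done but left out of 2a.* Item 4 taken at its word fits this. The separate secondary listing of GaitRite parameters is compatible with it but does not discriminate, since a TUG performed over the walkway could also produce those parameters.
- *Walkway time stands in for single-task TUG time.* No sentence says so, and it conflicts with the description of the dual-task trials as a repeat.

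**4. Consequence for the endpoint**

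Let S and D be single- and dual-task TUG time, W the single-task walkway time, and c = (D − S)/S the true cost. Under the first two readings both times come from one test and the cost is sound once that test is named. Under the third, the computed cost would be (D − W)/W = (S/W)(1 + c) − 1, which equals c only if S = W. The documents give neither S nor W, so no size can be attached to this.

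**5. Burden if single-task TUG trials had to be added**

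3 trials × 2 assessments per visit (before and after rTMS) × 3 visits = 18 trials per participant, or 6 per visit. Assuming 10 to 40 s per trial (not in the documents), plus the break of about 1 minute stated in 2a:
- per visit: 6 × (10 + 60)/60 = 7 min to 6 × (40 + 60)/60 = 10 min;
- as a share of the 2.5 h (150 min) session in Section 5: 7/150 = 4.7% to 10/150 = 6.7%.

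**6. Formula**

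The printed cost has no brackets round the numerator. Read literally it is D − S/S = D − 1. The intended (D − S)/S is clear, so this is clerical.

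**The case against.** The strongest reply is that this is loose naming and nothing more. Procedure 2a describes the dual-task trials as the same test done again, records a time in the single-task trials, and then calls the repeated test the TUG. On that reading a single-task time exists, tester and analyst work with the same test, and no bias follows.

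Much of this stands. It makes one common test the likeliest intent and mismatched tests the least supported reading. A reader might infer that testers and analysts will in fact use different tests, or that the comparison between stimulation sites is biased and could even change direction. The documents do not support either inference: both need walkway time to be substituted for single-task TUG time, which is nowhere planned.

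The reply does not remove the contradiction. A common test still has to be one thing or the other. If every trial is a walkway walk, the endpoint named in item 4 is never collected. If every trial is a TUG, the opening description in 2a is wrong. Either way at least one of the two places must be changed.

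**Conclusion.** The point holds as a contradiction between procedure 2a and item 4 about which motor test supplies the primary endpoint. If 2a is followed literally, there is no single-task TUG time and the dual-task cost cannot be computed as defined. Confidence in the mismatch of wording is high, since it rests on the text alone.

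It is not established that the wrong measurements will be taken or that the result will be biased. No numerical effect on the endpoint can be stated, because the plan gives no times. The number of visits or trials over which the same wording recurs is not a measure of harm: it is one gap in one procedure. It still needs repair before data are analysed, because the primary endpoint is involved and nothing else in the plan resolves it.

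**What to change.** Reconcile procedure 2a and item 4 before data are analysed, so that one named motor test is described once and timed in the same way in both conditions. The choice of test is the investigator's.

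- **If the TUG is intended:** describe the test and its timing in 2a, and set out single-task TUG trials beside the dual-task ones. This is wording only if such trials are already done. If not, it adds up to 3 short trials per assessment (18 per participant), to be weighed against the fatigue risk acknowledged in Section 7.
- **If the GaitRite walk is intended:** replace TUG with that walk time in 2a and item 4, and make clear that walk time is not also counted among the secondary GaitRite parameters. Item 4 does not list those parameters one by one, but 2a includes time among what the GaitRite records. This adds no trials, but it changes the named primary endpoint and so is more than an edit of wording.

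In either case print the cost as (dual − single)/single.
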